#### Tele-Coaching Adherence

Tele-coaching adherence will be defined as the proportion of planned exercise sessions in which a participant completes. The mean and associated 95% confidence interval will be reported.

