#### STUDY SCHEMA

Five weeks of weekly health coaching followed by either:

• Tapered health coaching (sessions only during weeks 8 and 11)

OR

• Continued weekly health coaching (sessions continue weekly through week 12)

Twelve weeks of home-based exercise including:

- two days/week of full-body muscle strengthening exercises
- · Aerobic activity aiming to achieve 150 mins/week

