# 3. Study Objectives and Endpoints

OBJECTIVES	ENDPOINTS
Primary	
-To evaluate changes in PWV following a 12-week home-based aerobic and muscle strengthening exercise program	-Within participant change from pre- to post- intervention as measured by carotid-femoral pulse wave velocity (PWV)
Secondary	
To evaluate changes in FMD following a 12-week home-based aerobic and muscle strengthening exercise program	-Within participant change from pre- to post- intervention as measured by brachial artery flow mediated dilation (FMD)
-To evaluate changes in the modifiable components of the ASCVD risk score (total cholesterol, HDL cholesterol, triglycerides, and systolic blood pressure) following the 12-week home-based comprehensive exercise program	-Within participant change of total cholesterol, HDL cholesterol, triglycerides, and systolic blood pressure from pre- to post-intervention
-To evaluate changes in functional fitness	-Within participant change of functional fitness from pre- to post-intervention as measured by the Functional Fitness Test
-To estimate muscle strengthening exercise session adherence	-Proportion of planned exercise sessions in which a participant completes at least 50% of prescribed exercises
-To estimate adherence to the aerobic physical activity guidelines (150 minutes/week)	-Proportion of planned weeks a participant accumulates 150 minutes of moderate intensity activity per week
-To estimate tele-coaching adherence	-Proportion of planned coaching sessions in which a participant completes
-To estimate acceptability	-Likert scale ratings of quality of exercise equipment, educational materials, health coaching, study feedback and distance delivery format
-To estimate changes in anthropometrics	-Within participant changes of waist and hip circumference, and weight from pre- to post-intervention
-To estimate changes in ambulatory activity levels	-Within participant change in average daily steps taken within a week from pre- to post-intervention as measured via ActiGraph accelerometer
-To estimate changes in psychosocial behavior change measures	-Within participant change of questionnaire scores (SEE, BPNES, PSS, BREQ-3) from pre- to post-intervention
-To estimate changes in diet	-Within participant change of questionnaire score (Multifactor Screener in Observing Protein and Energy Nutrition (OPEN)) from pre- to post- intervention

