#### 5. Study Design and Methods

#### 5.1 General Design

- A single arm exercise study
- The intervention itself is 12 weeks of exercise, with one week of accelerometer wear prior to
  exercise with an additional week to schedule post-study visit procedures, yielding a total
  intervention length of 14 weeks.
- The exercise intervention will consist of (a) in-person pre-intervention study measures; (b) instructional materials (e.g. detailed exercise manual) and exercise training equipment (e.g. resistance bands, adjustable pair of dumbbells, Fitbit Charge 5); (c) a virtually delivered instructional session; (d) access to informational web materials; (e) support and feedback provided via virtual health coaching sessions; and (f) in-person post-intervention study measures. Participants will also receive access to a study specific website (strivecardio-study.lab.uiowa.edu) that will include online versions of resources including video demonstrations, device support, exercise recommendations and study components.
- Health coaching sessions will be delivered virtually and consist of (a) an initial health coaching session during week one discussing the participant's visions for health and wellness and overall goals of completing the intervention exercises; (b) sessions delivered once per week through week four discussing progress, barriers, facilitators, self-efficacy, and motivations for exercise goals to facilitate exercise adoption; (c) a midpoint check-in including a non-bias report from their health coach describing their progress thus far in the intervention. Participants then have the personal option to continue meeting with their health coach on a weekly basis or taper their health coaching sessions to include only weeks eight and eleven; (d) a final in person health coaching session to conclude.

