SPPB. The short performance physical battery (SPPB) is a series of functional mobility assessments which measure balance, lower extremity strength, and fitness. Developed by the National Institute of Aging, the SPPB has clinically useful implications of predicting physical decline in older adults. The full battery utilizes standardized scoring, for a minimum of 0 points, to a maximum of 12 points, and includes the following three subscales: 1.) **Balance**. Each participant will stand for 10 seconds with their feet together, 10 seconds with their feet placed semi-tandem, and a final 10 seconds with their feet fully tandem. Participants receive a score from 0-4, based on their ability to attempt each position. 2.) **Repeated chair stand**, measuring lower extremity strength. Participants will stand up and sit down five times as quickly as they can. Participants receive a score of 0-4, based on total duration it takes to complete five total repetitions. 3.) **Gait speed**. Each participant will walk to a line placed on the floor three meters away at their typical walking pace. Participants receive a score from 0-4, based on total duration of walking this distance. **When collected:** Baseline, final visit (~14 weeks).

Exercise adherence. Adherence to intervention exercises will be measured via detailed exercise logs. A participant needs to complete at least 50% of the prescribed exercises in a session to be considered adherent to the session. **When collected:** ongoing, logs will be completed throughout the intervention and submitted at the final visit. Additionally, we will be monitoring participant's Fitbit data via Fitabase over the course of the study to monitor total physical activity and minutes of strength training logged.

Health coaching adherence. Adherence to health coaching will be monitored by the health coach on a weekly basis. A health coaching will be considered complete if the participant attends and participates in the health coaching session. Health coaches will also record the modality in which the session was completed, as well as the duration of completed sessions in minutes. **When collected:** ongoing, health coaches will record in REDCap whether a health coaching session was completed or not following each scheduled session.

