#### Muscle Strengthening Exercise Session Adherence

Exercise session adherence will be defined as the proportion of planned exercise sessions in which a participant completes at least 50% of the prescribed exercises. The mean and associated 95% confidence interval will be reported.

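### Section 7.2.3 defines tele-coaching adherence on exercise sessions instead of coaching sessions, and the Study Schema and schedule of events disagree on week 12 of the weekly option

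*Protocol*

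**What the plan says.** Estimating tele-coaching adherence is a listed secondary objective. Section 3 gives its endpoint as "Proportion of planned coaching sessions in which a participant completes". Section 6.1 (Health coaching adherence) supplies the completion rule, "A health coaching will be considered complete if the participant attends and participates in the health coaching session", and the data source: "health coaches will record in REDCap whether a health coaching session was completed or not following each scheduled session".

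Section 7.2.3 (Tele-Coaching Adherence) then states: "Tele-coaching adherence will be defined as the proportion of planned exercise sessions in which a participant completes". Two paragraphs earlier, the same section defines muscle-strengthening adherence as "the proportion of planned exercise sessions in which a participant completes at least 50% of the prescribed exercises".

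After five weekly sessions, each participant chooses one of two coaching options. The Study Schema describes them as "Continued weekly health coaching (sessions continue weekly through week 12)" and "Tapered health coaching (sessions only during weeks 8 and 11)". The schedule of events in Section 6 has one telehealth row per option. The weekly row is marked at baseline and weeks 1 to 11, and its week 12 and final-visit cells are empty. The tapered row is marked at baseline and weeks 1 to 5, 8 and 11.

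**The concern.** The protocol defines one endpoint twice, with two different units. The analysis section is the part most likely to be copied into a statistical analysis plan or a program, and it has the wrong one. Followed literally, it yields either a second exercise measure or a ratio of coaching sessions to exercise sessions. Neither is tele-coaching adherence.

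Correcting the unit leaves a second problem. An adherence proportion needs a fixed planned count, and for the weekly option two parts of the protocol disagree on whether a week-12 session is planned. At stake is one descriptive secondary endpoint with no success threshold.

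**Working it through.** **Step 1. The definitions side by side.**

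| Place | Measure | Unit |
|---|---|---|
| Section 3 | Tele-coaching adherence | Coaching sessions |
| Section 6.1 | Health coaching adherence | Coaching sessions, complete if attended and participated in |
| Section 7.2.3, Tele-Coaching | Tele-coaching adherence | Exercise sessions |
| Section 7.2.3, Muscle Strengthening | Strength-session adherence | Exercise sessions, with a 50% criterion |

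The tele-coaching rule agrees with the strength rule on the unit and disagrees with both places that describe coaching.

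**Step 2. What the literal rule would give.** There are two ways to apply it.

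- If numerator and denominator are both exercise sessions, the result repeats the strength measure without its 50% criterion and says nothing about coaching.
- If coaching sessions attended are divided by planned strength sessions, the denominator is 2 per week × 12 weeks = 24 (Section 6.3). Perfect coaching attendance would then score 12/24 = 50.0% or 11/24 = 45.8% on the weekly option, and 7/24 = 29.2% on the tapered option.

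**Step 3. Planned coaching sessions for each option.**

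- Weekly, Study Schema: weeks 1 to 12 = 12.
- Weekly, schedule of events: weeks 1 to 11 = 11 on-study sessions, or 12 marks if baseline is included.
- Tapered, Study Schema, schedule of events and Section 6.3: weeks 1 to 5 plus weeks 8 and 11 = 5 + 2 = 7.

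Counting the baseline mark makes the two weekly totals equal at 12, but they cover different weeks: baseline to week 11 in one place, weeks 1 to 12 in the other.

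The blank at week 12 is not a column shift. The table has 14 columns (baseline, weeks 1 to 12, final visit). The adverse-event row fills all 14. The ActiGraph row falls on baseline and week 12, as Section 6.1 says. The tapered row falls on weeks 8 and 11, as the text says.

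**Step 4. Size of the weekly-option conflict, with the unit corrected.** Take a participant who attends every session in weeks 1 to 11.

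- Denominator from the schedule of events: 11/11 = 100%.
- Denominator from the Study Schema, no week-12 session held: 11/12 = 91.7%.
- Difference: 8.3 percentage points.

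With 10 sessions attended, the figures are 10/11 = 90.9% and 10/12 = 83.3%, a difference of 7.6 points.

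If week 12 is both planned and held, full attendance is 12/12 = 100%. If it is neither planned nor held, full attendance is 11/11 = 100%. The fully attending participant therefore loses points only when week 12 is counted as planned but not held.

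**The case against.** The best defence is that the first part is a one-word slip that the protocol itself resolves. The paragraph is headed as tele-coaching adherence, the endpoint table names coaching sessions, and Section 6.1 says what counts as a completed one. That stands. A reader might infer that the trial will report no coaching figure, or that an exercise figure will appear in its place. The documents do not support that: the coaching data are recorded, and an analyst would have to ignore the heading and two other sections to go wrong. What survives is that the rule in the analysis section is incorrect as written.

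On the count, Section 6.1 has completion recorded after each scheduled session, so the number actually scheduled should be known for each participant. That also stands, and it limits the size. A reader might infer that the overall mean shifts by up to 8.3 points (0 if nobody chooses weekly, 4.2 if half do, 8.3 if all do). That range assumes that week 12 is counted but never held, that everyone attends fully otherwise, and a share choosing weekly that the protocol does not give. It is not a general consequence.

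Two further stronger readings should be set aside. The baseline telehealth mark and the closing in-person session of Section 5.1 might look like additional contradictions. Section 5.1 does place "an initial health coaching session during week one", which leaves the baseline mark unexplained, but Section 6.2 has a coach-led virtual orientation in the baseline accelerometer week. A session held in person is also not expected in a telehealth row. Whether either counts is a detail that a statistical analysis plan may settle. Nor does Section 5.1 independently confirm seven tapered sessions: it runs weekly sessions through week four and adds an undated midpoint check-in. The count of seven rests on the Study Schema, the schedule of events and Section 6.3.

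**Conclusion.** The point holds as a minor error. The tele-coaching rule in Section 7.2.3 uses the wrong unit and contradicts Sections 3 and 6.1, although the intended unit is recoverable from them. Separately, the Study Schema and the schedule of events conflict on week 12 of the weekly option, leaving 12 or 11 on-study sessions. The tapered option is consistent at 7.

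For a weekly-option participant with full attendance, the conflict is worth about 8 points, and only if a week-12 session counts as planned but is not held. The endpoint is descriptive, and the primary PWV analysis, sample size and power are unaffected. Which coaching schedule is right is not judged here.

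**What to change.** In Section 7.2.3 (Tele-Coaching Adherence), replace exercise sessions with coaching sessions. The measure then becomes coaching sessions completed under the Section 6.1 rule, divided by coaching sessions planned under the option that the participant chose. Reconcile the Study Schema and the weekly row of the schedule of events on week 12, so that the weekly denominator is fixed.

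The cost is wording only. Completion is already recorded in REDCap after each scheduled session, so no new data are needed.

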#### Acceptability

Acceptability will be assessed using Likert scale ratings of quality of exercise equipment, educational materials, health coaching, study feedback and distance-delivery format. Means and associated 95% confidence intervals will be reported for each item.

#### **Anthropometrics**

The within patient change of weight, waist and hip circumferences will be assessed from pre- to post-intervention. Mixed effects regression models will be used to estimate changes in anthropometrics. Random effects will be included to account for the longitudinally correlated nature of repeat measurements within a patient. Estimated mean changes and associated 95% confidence intervals will be reported.

#### Ambulatory Activity Levels

The within patient change in average daily steps taken within a week will be assessed from pre- to post-intervention. Mixed effects regression models will be used to estimate changes in ambulatory activity levels. Random effects will be included to account for the longitudinally correlated nature of repeat measurements within a patient. Estimated mean and associated 95% confidence interval will be reported.

#### Psychosocial Behavior Change

The within patient change in psychosocial behavior will be assessed from pre- to post-intervention. The SEE, BPNES, PSS, and BREQ-3 self-report questionnaires will be used to assess psychosocial behaviors. Mixed effects regression models will be used to estimate changes in questionnaire scores. Random effects will be included to account for the longitudinally correlated nature of repeat measurements within a patient. Estimated mean and associated 95% confidence interval will be reported.

#### **SPPB**

Mixed effects regression models will be used to estimate changes in each of the three tests included in the SBBP from pre- to post-intervention. We will follow standardized SPPB scoring for each of the three tests, with each individual test score ranging from 0-4. A total sum score for the entire battery of 0-12 will also be measured. Random effects will be included to account for the longitudinally correlated nature of repeat measurements within a patient. Estimated mean changes and associated 95% confidence intervals will be reported.

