-To evaluate changes in the short performance physical battery (SPPB)	-Within participant change from pre- to post- intervention as measured by the SPPB

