#### 4.2 Exclusion criteria

⊏XCIU	ision Criteria
1	Absolute contraindications to exercise (i.e., acute myocardial infarction, severe
orthor	pedic or musculoskeletal limitations)
2	History of previous myocardial infarction, ischemia, or hemorrhagic stroke
3	Medically documented history of heart disease including heart valve disease, coronary
artery	disease, heart failure, peripheral artery disease, aortic disease, pericardial disease,
cereb	rovascular disease, or deep vein thrombosis
4	Medical documentation of treatment-resistant hypertension OR taking 3 or more anti-

hypertensives with persistent hypertension

Medically documented history of cardiovascular disease including (but not limited to):
bypass surgery, stent procedures, bypass grafts, or coronary angioplasty

6 Medically documented or self-reported type 1 diabetes (insulin-dependents) Prescriptions for or use of semaglutide (GLP-1 agonists) including name brands: Ozempic, Wegovy or Mounjaro Current or recent (within last 3 months) use of hormone replacement therapy (HRT) Evidence of recurrent or metastatic disease Currently performing resistance training ≥2 days per week 10 11 Currently exceeding 150 minutes of at least moderate intensity exercise per week 12 Report of chest pain, shortness of breath, fainting, or angina pectoris 13 Self-reported history of falling, fall risk Have physical disability that would limit range of motion through exercises such as 14 sitting, standing and inability to walk one block Plans to move from the area 16 Enrolled in another clinical trial or has used of any investigational drugs, biologics, or devices within 30 days prior to study enrollment Self-reported tobacco use in last 7 days, current smoking, current tobacco use including e-cigarettes and vaping devices 18 Not suitable for study participation due to other reasons at the discretion of the investigator

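### SPPB change is analysed only on 0-4 category scores and their 0-12 total, so a ceiling of unknown size may hide change that the underlying chair-stand and gait times could show

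*Protocol*

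**What the plan says.** The SPPB paragraph of Protocol Section 7.2.3 sets the model and the scale: "Mixed effects regression models will be used to estimate changes in each of the three tests included in the SBBP" (the battery's initials are transposed there), "with each individual test score ranging from 0-4". It adds: "A total sum score for the entire battery of 0-12 will also be measured". Mean changes with 95% confidence intervals are to be reported. Section 3 lists within-participant SPPB change as a secondary endpoint, and the schedule places the battery at baseline and the final visit.

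Section 6.1 says how two of the three item scores arise. For the repeated chair stand: "Participants receive a score of 0-4, based on total duration it takes to complete five total repetitions". For gait over three metres: "Participants receive a score from 0-4, based on total duration of walking this distance". Balance is scored from three 10-second stances, and no timed alternative is described.

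On who is enrolled, Section 4.1 admits women aged 18 or over. Section 4.2 excludes "Self-reported history of falling, fall risk", as well as women whose disability limits sitting or standing or who cannot walk one block. Section 10.6.3 also excludes difficulty in rising from a chair, and presents the screen as a stand-in for basic function. Section 10.6.5 describes the battery as standardised for older adults and restricts it to women at low fall risk. Section 4.2 also excludes women who already do resistance training on two or more days a week or exceed 150 minutes of exercise a week.

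**The concern.** Two of the three item scores are coarse versions of a time. Every improvement within a category is lost, and a woman already in the top category can only stay there or fall. The trial looks for improvement, which is the direction that an upper bound blocks. The battery comes from work on decline in older adults. This trial takes adult women of any age and removes those with falls, fall risk or difficulty with sitting, standing or short walks, so low scorers should be under-represented.

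At stake is the reading of one secondary endpoint. If many women start at the maximum, a mean change near zero on the SPPB could reflect the scale and not the women. Beside improving fitness tests, such a result would be hard to interpret. The times behind the two scores have to be taken anyway, so the information is available at little cost.

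**Working it through.** **1. The plan's own figure.** The protocol gives no power, precision or expected distribution for the SPPB. Its only computed design figure is 93% power for pulse wave velocity (Section 7.1), which has no bearing on this point.

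**2. Inputs.**
- From the protocol: analysed n = 30 and 5% two-sided significance (both set in Section 7.1 for the primary endpoint and borrowed here); five-level item score 0-4 (Section 7.2.3).
- Assumed, because the protocol is silent: pre-post correlation ρ, true gain d in SD units of the timed performance, share p at the maximum at baseline, and lower cut points 0.75 SD apart.

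**3. Power on the continuous measure.** With two time points and complete pairs, the time effect is a paired comparison.
- SD of change = √(2(1 − ρ)) = √(2 × 0.3) = 0.775 for ρ = 0.7.
- Noncentrality = (d / SD of change) × √n = (0.4 / 0.775) × √30 = 2.83.
- Power from the noncentral t distribution with 29 degrees of freedom = 78%.

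**4. Power on the 0-4 score.** By simulation with 20,000 trials per setting: draw normal pairs with correlation ρ and shift d, place the top cut point so that a share p exceeds it at baseline, cut both visits into 0-4, and apply the paired t test to the score change.

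| Share at maximum at baseline | Time | 0-4 score |
|---|---|---|
| 10% | 78% | about 69% |
| 30% | 78% | about 63% |
| 50% | 78% | about 52% |
| 70% | 78% | about 33% |
| 85% | 78% | about 16% |

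**5. Sensitivity to the assumptions.** Power on the score at 10%, 30%, 50%, 70% and 90% at maximum:

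| Gain, correlation | Time | 10% | 30% | 50% | 70% | 90% |
|---|---|---|---|---|---|---|
| 0.3 SD, 0.8 | 71% | 58% | 52% | 41% | 26% | 7% |
| 0.5 SD, 0.5 | 75% | 68% | 64% | 53% | 37% | 10% |
| 0.7 SD, 0.5 | 96% | 92% | 88% | 79% | 58% | 14% |

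The 0.7 SD row is close to the lower-body effect size of 0.71 that Section 2 reports from the sponsor's ten-participant study.

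**6. The same point without power.** The plan is to report estimates, so the expected mean change matters too. For one and the same true gain of 0.5 SD, the mean change on the 0-4 score is 0.58, 0.49, 0.37, 0.23 and 0.08 points with 10%, 30%, 50%, 70% and 90% at maximum. The reported effect therefore depends on where women start as well as on what they gain.

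**7. Limits of the check.** It covers one timed item. The 0-12 total was not simulated. It is the sum of three bounded items and has its own upper limit.

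**The case against.** The strongest reply has four parts.

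*No ceiling is documented.* A reader might infer that a ceiling does hide change, or that the women were screened for good mobility. The protocol supports neither. It gives no SPPB data, and Section 10.6.3 presents the screen as a check of basic function, which removes low performers without selecting high ones. Section 4.2 also excludes women who are already active, and Sections 1 and 2 describe a group with much obesity, metabolic disease and treatment effects. This stands: the ceiling is a possibility, and its size is an assumption.

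*Other endpoints cover the ground.* A reader might infer that the trial would miss gains in leg strength or walking. It would not. The Functional Fitness Test includes a 30-second chair stand, a 6-minute walk and an 8-foot up-and-go, measured as counts, distance and time, and Section 7.2.3 models each test of that battery. This stands and limits the consequence. It does not repair the SPPB endpoint, and usual-pace gait speed has no exact counterpart there.

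*Standard scoring is legitimate.* The plan follows the battery's own scoring, claims no SPPB power, and an unseen statistical analysis plan could add the times. Using the standard score is indeed no error, and replacing it would be debatable. But the protocol states which scale is analysed, and information is lost on that scale even when few women are at the top.

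*The seconds may not be kept.* Section 6.1 bases the scores on durations but does not say that the raw values are stored. This stands and belongs in the fix.

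**Conclusion.** The point holds in a limited form. The stated analysis uses only bounded category scores, although two of the three items rest on times taken at both visits. A woman at 4 on an item cannot show improvement on it, and eligibility makes low scores less likely, so a ceiling may hide change.

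The size cannot be fixed from the protocol. With 30 women, correlation 0.7 and a gain of 0.4 SD, power falls from about 78% on the time to about 69% on the score if 10% start at the maximum, and to about 16% if 85% do. The score was the weaker measure in every setting tried. The loss was modest when few women start at the top and severe only when most do. All of this rests on assumed correlations, gains, cut points and ceiling shares.

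The consequence is confined to one of twelve secondary objectives in a pilot whose primary endpoint is pulse wave velocity. It is worth correcting because the correction is cheap.

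**What to change.** In the SPPB part of Section 6.1, state that chair-stand time in seconds and 3-metre gait time are recorded at both visits. In Section 7.2.3, add change in these two measures (as time, or as speed for gait) as continuous outcomes in the same mixed model, alongside the standard 0-4 item scores and the 0-12 total. Report how many women are at the maximum at baseline for each item and for the total, so that a small mean change can be interpreted. Balance stays on its score.

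The cost is a few sentences, two extra secondary estimates, and a check that raw seconds are stored. No test or visit is added. If only the scores have been entered so far, it should be established whether the times can be recovered from source records.
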